5.5 CRITERIA FOR TEMPORARILY DELAYING ENROLLMENT/ADMINISTRATION OF STUDY INTERVENTION

During a regional or national emergency declared by a governmental agency, if the site is unable to adequately follow protocol mandated procedures, contingency measures are proposed in [Section 10.9](#).

6 STUDY INTERVENTION(S) AND CONCOMITANT THERAPY

Study intervention is defined as any investigational intervention(s), marketed product(s), intended to be administered to a study participant according to the study protocol.

6.1 STUDY INTERVENTION(S) ADMINISTERED

Participants will receive study treatment until PD, unacceptable toxicity, other permanent discontinuation criteria as described in [Section 7](#), or completion of the maximum cycles allowed in the substudies. However, treatment beyond PD may be allowed for up to 9 weeks if the participant appears to be benefiting clinically after discussion with the Sponsor.

6.1.1 Investigational medicinal product

Details of SAR444245 are shown in [Table 3](#).

Preparation and administration of investigational medicinal product (IMP) are detailed in the pharmacy manual.

Hydration is required for SAR444245 infusions. Details are provided in [Section 6.1.3](#).

Table 3 - Overview of IMP administered

Intervention name	SAR444245
Type	Biologic
Dose formulation	Concentrate for solution for infusion
Unit dose strength(s)	2.0 mg/mL
Dosage level(s)^a	24 µg/kg (or reduced to █ µg/kg or another lower dose level recommended by Study Board)
Route of administration	IV infusion
Use	Experimental
IMP or NIMP	IMP
Packaging and labeling	Supplied in a single-dose vial in a treatment box. Each vial contains 2 mg/mL with an extractable volume of 1 mL. Each vial and treatment box will be labeled as required per country requirement.
Current/Former name(s) or alias(es)	NA

^a The total dose will be calculated based on the weight on the day of the infusion or the most recent weight assuming it was assessed in a reasonable time frame according to Investigator assessment. Study sites should make every effort to measure body weight as close to the infusion day as possible considering the variability of local process from site to site. If the infusion is prepared with the most recent weight assessed in a reasonable time frame, the participant must still be weighed on D1 of each cycle, and the weight recorded in the e-CRF. Study sites should make every effort to target infusion timing to be as close to 30 minutes as possible. However, given the variability of infusion pumps from site to site, a window of -5 minutes and +10 minutes is permitted.

6.1.2 Non-investigational medicinal products

Non-investigational medicinal products (NIMP) include the premedication administered for SAR444245.

6.1.2.1 *Premedication for SAR444245*

[figure not shown]
All participants will receive the following premedication to prevent or reduce the acute effect of infusion-related reactions (IRR) or flu-like symptoms, 30 to 60 minutes prior to SAR444245 infusion (no longer than 60 minutes) for the first 4 cycles:

[figure not shown]
- Acetaminophen (paracetamol) 650 to 1000 mg (IV or PO) (or equivalent), and then optionally thereafter as needed.
- Diphenhydramine 25 to 50 mg IV or PO (or equivalent eg, cetirizine, promethazine, dexchlorpheniramine, according to local approval and availability), and then optionally thereafter as needed.

SAR444245 premedication may be optional after 4 cycles:

- For a participant who has no IRR for the first 4 cycles, premedication for the subsequent infusions is optional at the Investigator's discretion. However, if during the subsequent infusions without premedication the participant experiences an IRR (any grade), premedication must be restarted for all subsequent infusions.
- If a participant develops an IRR Grade <2 during their first cycle only and then experiences no further IRRs during their next 3 cycles the Investigator may consider omitting premedication for Cycle 5. If no IRR is observed during Cycle 5 without premedication, premedication is optional for the subsequent cycles at the Investigator's discretion. However, if during Cycle 5 without premedication the participant experiences an IRR (any grade), premedication must be restarted for all subsequent cycles.

6.1.3 Hydration guidelines for SAR444245 administration

6.1.4 Readiness for treatment of severe cytokine release syndrome

Doses of tocilizumab or alternative therapies per site practice in CRS management should be available at site at all times in the event that a participant requires rapid intervention for the treatment of severe CRS. Please refer to the individual substudies for detailed guidelines for the management of CRS.

6.2 PREPARATION/HANDLING/STORAGE/ACCOUNTABILITY

1. The Investigator or designee must confirm appropriate temperature conditions have been maintained during transit for all study intervention received and any discrepancies are reported and resolved before use of the study intervention.
2. Only participants enrolled in the study may receive study intervention and only authorized site staff may supply or administer study intervention. All study intervention must be stored in a secure, environmentally controlled, and monitored (manual or automated) area in accordance with the labeled storage conditions with access limited to the Investigator and authorized site staff.
3. The Investigator, institution, or the head of the medical institution (where applicable) is responsible for study intervention accountability, reconciliation, and record maintenance (ie, receipt, reconciliation, and final disposition records).

Any quality issue noticed with the receipt or use of an IMP (deficiency in condition, appearance, pertaining documentation, labeling, expiration date, etc) must be promptly notified to the Sponsor. Some deficiencies may be recorded through a complaint procedure (see [Section 8.3.9](#)).

A potential defect in the quality of IMP may be subject to initiation of a recall procedure by the Sponsor. In this case, the Investigator will be responsible for promptly addressing any request made by the Sponsor, in order to recall the IMP and eliminate potential hazards.

Under no circumstances will the Investigator supply IMP to a third party, allow the IMP to be used other than as directed by this clinical trial protocol, or dispose of IMP in any other manner.

Treatment preparation and administration (including compatible materials) will be further detailed in the pharmacy manual.

6.3 MEASURES TO MINIMIZE BIAS: RANDOMIZATION AND BLINDING

Not applicable.

6.4 STUDY INTERVENTION COMPLIANCE

Participants must be dosed at the site and will receive IMP directly from the Investigator or designee, under medical supervision. The person responsible for drug dispensing is required to maintain adequate records of the IMP administration. These records include the date the IMP components are received from the Sponsor, dispensed to the participant and destroyed or returned to the Sponsor. The packaging batch number and the treatment number on the vial must be recorded on the drug accountability form. The date and time of each dose administered in the clinic will be recorded in the source documents and recorded in the e-CRF. The dose of study intervention and study participant identification will be confirmed at the time of dosing by a member of the study site staff other than the person administering the study intervention.

6.5 DOSE MODIFICATION

Refer to individual substudy for details.

6.6 CONTINUED ACCESS TO INTERVENTION AFTER THE END OF THE STUDY

There will be no intervention beyond the end of the study.

6.7 TREATMENT OF OVERDOSE

There is no specific antidote for overdose with SAR444245.

If overdose occurs (see [Section 8.3.8](#) for definitions), symptomatic management is indicated.

Treatment of overdose should consist of general supportive care with aggressive fluid management, if clinically indicated.

Procedures for treating symptoms and complications of immune-related adverse events (irAEs) are provided in the individual substudies.

In the event of an overdose, the Investigator should:

1. Contact the Sponsor immediately.
2. Closely monitor the participant for any AE/SAE and laboratory abnormalities until study intervention can no longer be detected systemically (at least 3 months).
3. Obtain a plasma sample for PK analysis right after the overdose event is identified (only if an overdose is identified within 5 days from start of overdose infusion).
4. Document appropriately in the e-CRF.

Decisions regarding dose interruptions or modifications will be made by the Investigator in consultation with the Sponsor based on the clinical evaluation of the participant.

6.8 CONCOMITANT THERAPY

Any medication or vaccine (including over-the-counter or prescription medicines, vitamins, and/or herbal supplements, or other specific categories of interest) that the participant is receiving at the time of enrollment or receives during the study must be recorded along with:

- Reason for use
- Dates of administration including start and end dates

The Sponsor should be contacted if there are any questions regarding concomitant or prior therapy.

Medications or vaccinations specifically prohibited in the exclusion criteria are not allowed during the ongoing trial. If there is a clinical indication for any medication or vaccination specifically prohibited during the trial, discontinuation from study intervention may be required. The Investigator is to discuss prohibited medication/vaccination with the Sponsor. The final decision on any supportive therapy or vaccination rests with the Investigator and/or the participant's primary physician. However, the decision to continue the participant on trial therapy schedule requires the mutual agreement of the Investigator, the Sponsor, and the participant.

6.8.1 Acceptable concomitant medications

All treatments that the Investigator considers necessary for a participant's welfare may be administered at the discretion of the Investigator in keeping with the community standards of medical care. All concomitant medication will be recorded on the electronic case report form (e-CRF) including all prescription, OTC, herbal supplements, and IV medications and fluids. If

changes occur during the trial period, documentation of route, and date will also be included on the e-CRF.

Palliative and supportive care is permitted during the course of the trial for underlying medical conditions and management of symptoms. Surgery or radiotherapy for tumor control is not permitted during the study; however, radiotherapy or procedures for symptom management is allowed after discussion with and approval by the Sponsor.

All concomitant medications received within 28 days before the first dose of trial treatment through the Follow-up Visit should be recorded.

Colony-Stimulating Factors

Routine use of colony-stimulating factors (CSFs) is not permitted. American Society of Clinical Oncology guidelines for use of CSFs should be followed ([32](#)).

6.8.2 Prohibited concomitant medications

Participants are prohibited from receiving the following therapies during the Screening and Treatment Period of this trial:

- Antineoplastic systemic chemotherapy or biological therapy not specified in this protocol.
- Immunotherapy not specified in this protocol.
- Investigational agents other than specified in this protocol.
- Radiotherapy for tumor control (please refer to [Section 6.8.1](#) for allowed radiotherapy).
- Live or live attenuated virus vaccines within 28 days prior to the first dose of trial treatment and while participating in the trial. Examples of live-virus vaccines include, but are not limited to, the following: measles, mumps, rubella, chickenpox, yellow fever, seasonal flu (seasonal flu vaccines that do not contain live virus are permitted), nasal H1N1 flu, rabies, Bacillus Calmette–Guérin (BCG), and typhoid.
- Systemic glucocorticoids and other immunosuppressive therapies such as anti-TNF, anti-IL6, etc, except for:
 - Use in premedication defined in the study protocol,
 - Treatment of immune-mediated AEs when indicated (irAE, CRS, ICANS, IRR, see details in the substudies),
 - Treatment of any life-threatening emergency,
 - Physiologic replacement as long as they are not being administered for immunosuppressive intent, and
 - A brief course (≤ 7 days) of systemic corticosteroid for prophylaxis (eg, contrast dye allergy) or for the treatment of non-autoimmune conditions (eg, delayed-type hypersensitivity reactions caused by contact allergen).

Participants who, in the assessment by the Investigator, require the use of any of the aforementioned treatments for clinical management should be removed from the trial. Participants may receive other medications that the Investigator deems to be medically necessary.

The exclusion criteria describe other medications which are prohibited in this trial.

There are no prohibited therapies during the Observation and Survival Follow-up Period.

For withholding antihypertensive medications as part of hydration guidelines, please refer to [Section 6.1.3](#).

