safety (as per Schedule of Activities [SoA] in the individual substudy) and tumor imaging assessments, until PD, start of another anticancer therapy, final cohort cut-off, whichever comes first, before moving to the Survival Phone Call Follow-Up Period.

2. Participants who discontinue study treatment **with PD** (per Lugano response criteria 2014[2]) will be followed for safety in the Follow-Up Visit 1 occurring 3 months ± 7 days from last IMP administration, before moving to the Survival Phone Call Follow-Up Period.

Participants who move into the **Survival Phone Call Follow-up Period** will be contacted by telephone every 3 months ± 14 days to assess for survival status. Updated survival status may be requested by the Sponsor at any time during the study. Survival Phone Call Follow up will continue until death, participant request to discontinue from follow-up, or cut-off date for final analysis has been reached, or upon cancellation of Survival follow-up at the discretion of the Sponsor at any prior timepoint.

After the cohort cut-off date for the primary analysis, participants can continue to receive IMP, if clinical benefit is observed, until full permanent discontinuation criteria described in [Section 7](#) are met and will continue to undergo all assessments as per the study schedule of activities in the individual substudy.

For each cohort, the cut-off date for the final analysis (ie, analysis of secondary objectives and update of the primary objective) will be 3 years from cohort last participant in (LPI).

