7 DISCONTINUATION OF STUDY INTERVENTION AND PARTICIPANT DISCONTINUATION/WITHDRAWAL

7.1 DISCONTINUATION OF STUDY INTERVENTION

7.1.1 Permanent discontinuation

Study intervention should be permanently discontinued in any of the following cases:

- At the participant's request, at any time and irrespective of the reason (consent's withdrawal), or at the request of their legally authorized representative. "Legally authorized representative" is considered to be an individual or judicial or other body authorized under applicable law to consent on behalf of a prospective participant to the patient's participation in the procedure(s) involved in the research.
- If, in the Investigator's opinion, continuation of the study treatment would be detrimental to the participant's wellbeing, such as:
 - Unacceptable AE.
 - Documented disease progression
 -
 - Poor compliance to the study protocol.
 - Other, such as concurrent illness, that prevents further administration of study intervention, or that in the Investigator's opinion, in the best interest of the participant.
- In case of pregnancy occurrence.

If study intervention is permanently discontinued, the participant will remain in the study to be evaluated for serial tumor assessment if permanent discontinuation is not due to PD, for safety assessment as per SoA in the individual substudy and until resolution or stabilization of AE, and any other assessment as per SoA. Data to be collected at the time of discontinuation of study intervention and follow-up and for any further evaluations that need to be completed are reported in the SoA.

7.1.1.1 *Unacceptable adverse events leading to permanent intervention discontinuation*

Discontinuation of study intervention for abnormal liver function should be considered by the Investigator when a participant meets one of the conditions outlined in the dose modification and toxicity management guidelines (see individual substudy protocols), or if the Investigator believes that it is in best interest of the participant.

If a clinically significant finding is identified after enrollment, the Investigator or qualified designee will determine if the participant can continue in the study and if any change in participant management is needed. This review of the electrocardiogram (ECG) printed at the time of collection must be documented. Any new clinically relevant finding should be reported as an AE.

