Any potentially clinically significant abnormal laboratory value or ECG parameter will be immediately rechecked for confirmation and repeated after 24 hours to document evolution before making a decision of permanent intervention discontinuation for the concerned participant.

Decision criteria for discontinuation following immune-mediated AEs are described in the individual substudy (Guidelines for the management of IRR, CRS, ICANS, VLS).

If participants are clinically stable, and possibly deriving clinical benefit from therapy with minimal toxicity, they will be maintained on treatment.

See the SoA in the individual substudy for data to be collected at the time of intervention discontinuation and follow-up and for any further evaluations that need to be completed.

Handling of participants after permanent intervention discontinuation

Participants will be followed-up according to the study procedures specified in this protocol up to the scheduled date of study completion, or up to recovery or stabilization of any AE to be followed-up as specified in this protocol, whichever comes last.

If possible, and after the permanent intervention discontinuation, the participants will be assessed using the procedure normally planned for the last dosing day with the IMP including a pharmacokinetics sample, if appropriate. Tumor assessment should be repeated if not done at the last cycle.

All cases of permanent intervention discontinuation must be recorded by the Investigator in the appropriate pages of the e-CRF when considered as confirmed.

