7.2 PARTICIPANT DISCONTINUATION/WITHDRAWAL FROM THE STUDY

- A participant may withdraw from the study at any time at his/her own request (or at their legally authorized representative's request), or may be withdrawn at any time at the discretion of the Investigator for safety, behavioral or compliance reasons. This is expected to be uncommon.
- At the time of discontinuing from the study. See SoA for data to be collected at the time of study discontinuation and follow-up and for any further evaluations that need to be completed.
- The participant will be permanently discontinued both from the study intervention and from the study at that time.
- If the participant withdraws consent for disclosure of future information, the Sponsor may retain and continue to use any data collected before such a withdrawal of consent.
- If a participant withdraws from the study, he/she may request destruction of any samples taken and not tested, and the Investigator must document this in the site study records.

If participants no longer wish to take the IMP, or their legally authorized representative(s) no longer wish the participant to take it, they will be encouraged to remain in the study.

The Investigators should discuss with them key visits to attend. The value of all their study data collected during their continued involvement will be emphasized as important to the public health value of the study.

Participants who withdraw from the study intervention should be explicitly asked about the contribution of possible AEs to their decision, and any AE information elicited must be documented.

All study withdrawals should be recorded by the Investigator in the appropriate screens of the e-CRF and in the participant's medical records. In the medical record, at least the date of the withdrawal and the reason should be documented.

In addition, a participant (or their legally authorized representative) may withdraw his/her consent to stop participating in the study. Withdrawal of consent for intervention should be distinguished from withdrawal of consent for follow-up visits and from withdrawal of consent for non-participant contact follow-up, eg, medical record checks. The site should document any case of withdrawal of consent.

Participants who have withdrawn from the study cannot be re-included in the study. Their inclusion and intervention numbers must not be reused.

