8.3.1 Time period and frequency for collecting AE and SAE information

All AEs, including adverse events of new onset, as well as worsening of baseline signs and symptoms will be collected throughout study period, from the signing of the informed consent form (ICF) until **30 days** following cessation of study treatment.

All SAEs and AESIs will be collected throughout the study period, from the signing of the informed consent form (ICF) until **3 months** following last administration of study treatment.

All SAEs and AESI will be recorded and reported to the Sponsor or designee immediately and under no circumstance should this exceed 24 hours, as indicated in Appendix 3 ([Section 10.3](#)). The Investigator will submit any updated SAE data to the Sponsor within 24 hours of it being available.

Investigators are not obligated to actively seek information on AEs or SAEs after conclusion of the study participation. However, if the Investigator learns of any SAE, including a death, at any time after a participant has been discharged from the study, and he/she considers the event to be reasonably related to the study intervention or study participation, the Investigator must promptly notify the Sponsor.

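### Master protocol 6.8.2 tells sites to take participants who need a prohibited treatment out of the trial, whereas 7.1.1 and 4.1 keep those who stop IMP in follow-up

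*Protocol*

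**What the plan says.** Section 6.8.2 of the master protocol lists treatments barred during Screening and Treatment: other anticancer therapy (including tumor-control radiotherapy), investigational agents, live vaccines, and systemic steroids or other immunosuppressants outside named exemptions. It then says that participants who, in the Investigator's assessment, "require the use of any of the aforementioned treatments for clinical management should be removed from the trial". The same section ends: "There are no prohibited therapies during the Observation and Survival Follow-up Period".

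Other current text on stopping treatment or leaving the study:

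- **6.8:** "If there is a clinical indication for any medication or vaccination specifically prohibited during the trial, discontinuation from study intervention may be required". It also lets trial therapy continue if Investigator, Sponsor and participant all agree.
- **7.1.1:** "If study intervention is permanently discontinued, the participant will remain in the study to be evaluated for serial tumor assessment", provided that the stop was not for PD, and for safety assessment.
- **7.1.1.1** (handling after permanent discontinuation): "Participants will be followed-up according to the study procedures specified in this protocol up to the scheduled date of study completion", or until AEs recover or stabilize, whichever is later.
- **4.1:** participants who stop without PD have safety visits and "tumor imaging assessments, until PD, start of another anticancer therapy, final cohort cut-off, whichever comes first", then survival calls.
- **7.2**, on withdrawal from the study: "The participant will be permanently discontinued both from the study intervention and from the study at that time". Withdrawn participants cannot re-enter.
- **8.3.1:** "All SAEs and AESIs will be collected throughout the study period", up to three months after the last dose. Substudy 01 applies the same three months to irAEs in Cohort A, whether or not another anticancer therapy has begun.
- **SAP 3.2.2 and 3.3.1.2:** response, DoR and PFS use tumor assessments regardless of IMP discontinuation, but only up to any new anticancer therapy.

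**The concern.** The protocol separates stopping treatment (7.1) from leaving the study (7.2). For a participant who needs a prohibited drug, 6.8.2 uses the language of leaving the study where the rest of the plan calls for stopping treatment. A site that follows the sentence as written would withdraw the participant, and 7.2 makes that irreversible.

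For a treated participant without PD, the remaining scans, the rest of the SAE/AESI window (and the irAE window in Cohort A) and the survival calls would all be lost. The participant would still count in the efficacy denominator, because permanent discontinuation of treatment is enough to enter the efficacy population (master protocol 9.3; SAP Table 4). PFS, or DoR for a responder, would be censored at the last evaluable scan (SAP Table 5) when the SAP intended follow-up to continue.

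**Working it through.** No stated design figure depends on this sentence, so the check is mainly a comparison of text.

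**1. Which sections conflict with 6.8.2, and how strongly**

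- 7.1.1, 7.1.1.1 and 4.1 conflict directly: they say that a participant whose treatment stops stays in follow-up.
- 6.8 is inconsistent in a narrower way. It does not mention follow-up; it limits the consequence to study intervention and allows continuation by agreement.
- 8.3.1 and the SAP retain nobody. One sets a collection window and the other says how tumor data are used after IMP stops. Both assume that the participant is still being followed.

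**2. Which data are exposed, by class of treatment**

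- *New anticancer therapy.* 4.1 already ends imaging, and the SAP already ends response assessment and censors DoR and PFS. Removal costs no analysed tumor data. It does cost safety data, because 8.3.1 has no stop at new anticancer therapy, and it costs the survival calls to which 4.1 moves these participants.
- *Non-exempt steroids or immunosuppressants, and live vaccines.* These are not anticancer therapy, so the treatment-policy strategy applies in full and tumor data are exposed as well. Exempt uses (immune-mediated AEs, life-threatening emergencies, physiologic replacement, protocol premedication, corticosteroid courses of at most 7 days for prophylaxis or non-autoimmune conditions) do not trigger the sentence.
- *Screening.* There is no IMP to stop, and 5.4 already covers screen failure, including the temporary kind.

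**3. Scale for one participant (not an expected loss)**

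- Response: each cohort plans N=25, so one response not observed is 1/25 = 4 percentage points. Recomputed exact 90% Clopper-Pearson limits match the documents' sample-size tables: 5/25 = 20% (8.2% to 37.5%) and 4/25 = 16% (5.7% to 33.0%).
- Safety window: at the SAP's 30.4375 days per month, three months is 3 × 30.4375 = 91.3 days. Removal at the nominal end-of-treatment visit (day 30) leaves 91.3 − 30 = 61.3 days uncollected. With the visit's ±7-day window this is 91.3 − 37 = 54.3 to 91.3 − 23 = 68.3 days. Earlier removal loses more.
- Scans: no count is given. It would depend on an assumed removal date, on how long the participant stays progression-free, and on whether the three-monthly schedule in 4.1 or the 9- then 12-weekly schedule in 8.1.1 applies.

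**The case against.** The strongest reply is that context settles the meaning. The prohibitions cover only Screening and Treatment. The closing line of 6.8.2 lifts them in follow-up, which makes sense only if recipients are expected to be there. The parent section 6.8 speaks of study intervention and requires discussion with the Sponsor. Needing a prohibited drug is not a named withdrawal reason in 7.2. This stands as evidence of intent. It does not change the operative sentence, and 7.2 allows Investigator withdrawal for safety or compliance reasons, so the literal reading has a ready route.

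It can also be said that few participants are involved, that a response first seen during a long steroid course would be hard to credit to IMP, that survival calls may be cancelled by the Sponsor and overall survival is not among the visible primary or secondary endpoints, and that under 8.3.1 related SAEs learned of after discharge must still be reported. All of this stands. It keeps the point small and leaves PFS/DoR follow-up and active safety collection as the clearer losses.

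A reader might infer more: that 6.8, 8.3.1 and the SAP each independently require retention, or that the primary endpoint is materially biased. The documents do not support either. Retention comes from 7.1.1, 7.1.1.1 and 4.1. New anticancer therapy already ends response assessment, and nothing indicates how often a non-exempt steroid, immunosuppressant or live vaccine would be needed.

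**Conclusion.** The inconsistency is real and minor. As written, the instruction in 6.8.2 contradicts 7.1.1, 7.1.1.1 and 4.1, does not fit 6.8, and would undercut data collection that 8.3.1 and the SAP presuppose. Stopping IMP is very likely what was meant.

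Harm arises only if a site applies the sentence literally to a treated participant. For tumor data the exposed group is in practice those needing non-exempt steroids or immunosuppressants, or live vaccines; this takes the investigational-agent class to mean anticancer agents. For SAE/AESI data, and irAE data in Cohort A, any prohibited class is exposed. Few participants are likely to be affected, no expected loss can be quantified from the documents, and no sample-size or precision figure changes.

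**What to change.** In 6.8.2, replace the instruction to remove such participants from the trial with:

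> *should be discontinued from study intervention, subject to Section 6.8, and, if any IMP has been received, remain in the study for tumor, safety and survival follow-up per Sections 4.1, 7.1.1 and 8.3.1; participants not yet enrolled are handled per Section 5.4.*

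The reference to 6.8 preserves the existing agreement route without restating it. Tying follow-up to receipt of IMP covers participants who are enrolled but not dosed. The reference to 5.4 leaves the temporary screen-failure route intact.

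The cost is one sentence at the next protocol amendment. No visit, scan or data item is added, since all of this follow-up is already planned, and the SAP needs no change.
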